6.11.1.3 Sensitivity Analyses

6.11.1.3.1 Pattern-Mixture Model

To assess the robustness of the results to deviations from the MAR assumption in the primary analysis, a sensitivity analysis will be conducted such that non-monotone missing data is imputed under the MAR assumption while the monotone data is imputed under the missing not at random (MNAR) assumption (i.e., that missingness is also dependent on the unobserved variable values).

This analysis will therefore provide a stress test of the MAR assumption in the primary analysis and will provide a conservative estimate of the treatment effect.

The pattern-mixture modeling will be implemented by first turning the non-monotone missing data pattern into a monotone missing pattern under the MAR assumption using the Markov Chain Monte Carlo (MCMC) method in SAS' PROC MI with the IMPUTE = MONOTONE and the PRIOR = JEFFREYS options to specify a non-informative prior for the imputation process. Then the MONOTONE statement along with the MNAR statement with option MODEL in SAS' PROC MI will be utilized to implement the MNAR assumptions and control-based pattern imputation^{2,3}. The inference of this sensitivity analysis will be based on the combined estimates using the standard multiple imputation technique via Rubin's⁴ rules.

Missing data will be imputed using a pattern-mixture model approach that uses a control-based pattern imputation. With this approach, subjects who discontinued from the NYX-2925 treatment group will be assumed to follow a similar outcome trajectory as subjects from the placebo (control) group, and subjects who discontinued from placebo (control) group are modeled as completers within their own group (MAR within control group). That is, the imputation model for the missing observations in the NYX-2925 treatment group is constructed not from the observed data in the NYX-2925 treatment group, but rather from the observed data in the placebo group. This model is also the imputation model that will be used to impute missing observations in the placebo group. The missing values for each variable will be imputed based on a model simulated from the posterior predictive distribution of the conditional regression model fitted on the imputed variable using only the observations from the placebo group. This will be implemented by utilizing the MONOTONE REG statement and MNAR statement with option MODEL of SAS' PROC MI with options nimpute=20 and seed=373613962.

The following is the sample SAS code that will be used to implement the control-based pattern mixture imputation:

```
PROC MI DATA=DATAIN OUT=DATAIN_MONO SEED=373613962 NIMPUTE=1;
BY TREATMENT;
VAR BASELINE NRS_Week1-NRS_Week12;
MCMC CHAIN=MULTIPLE IMPUTE=MONOTONE PRIOR = JEFFREYS;
RUN;
PROC MI DATA= DATAIN_MONO SEED=373613962 NIMPUTE=20
OUT=DATA_IMPUTED;
CLASS TREATMENT SITE;
MONOTONE REG(NRS_Week1-NRS_Week12);
MNAR MODEL(NRS1_Week1-NRS_Week12 /
MODELOBS=(TREATMENT='Placebo'));
VAR SITE BASELINE NRS_Week1-NRS_Week12;
RUN;
```

Once all the weekly mean NRS scores are imputed, the change from baseline at each week will be calculated and consequently will be analyzed using the same MMRM model employed in the primary analysis.

The following sample SAS code will be used:

```
PROC MIXED DATA= IMPUTED_ALL;

BY _IMPUTATION_; /* 20 sets of results produced */

CLASS USUBJID TREATMENT WEEK SITE;

MODEL CFB = TREATMENT WEEK SITE TREATMENT*WEEK BASELINE /

DDFM=KR;

REPEATED WEEK / SUBJECT=USUBJID TYPE=UN;

LSMEANS TREATMENT TREATMENT*WEEK / CL DIFF;

ODS OUTPUT LSMEANS=LSMEANS DIFFS=DIFFS;

RUN;
```

Then the results are to be summarized using PROC MIANALYZE, where the treatment group LS means and their differences between treatments will be combined across all 20 imputed datasets:

```
PROC SORT DATA= LSMEANS; BY TREATMENT WEEK _IMPUTATION_; RUN;

PROC MIANALYZE PARMS= LSMEANS;

MODELEFFECTS ESTIMATE;

STDERR STDERR;

ODS OUTPUT PARAMETERESTIMATES= LSMEANS_COMB;

BY TREATMENT WEEK;

RUN;

PROC SORT DATA= DIFFS; BY TREATMENT;

RUN;

PROC MIANALYZE PARMS= DIFFS (WHERE=(WEEK=_WEEK));

MODELEFFECTS ESTIMATE;

STDERR STDERR;

ODS OUTPUT PARAMETERESTIMATES= DIFFS_COMB;

BY TREATMENT;

RUN;
```

LS means, SEs, and 95% CIs for each treatment group based on the imputed data will be presented at each week as well as the estimate of treatment difference, SE, and p-value at each week with Week 12 as the primary timepoint of interest.

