4 SAMPLE SIZE

The planned sample size is a total of 204 randomized subjects. This will provide approximately 80% power to detect a difference in means of 0.73 assuming that the common standard deviation is 1.7 (and accounting for 15% drop-out rate), using two-sided statistical testing with an overall Type I error rate of 0.05.

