5 RANDOMIZATION

Pain scores reported by subjects during the Screening Period will be evaluated by the Interactive response technology (IRT) system for raw score and for variability among scores after transmission of pain scores from the handheld devices to determine randomization eligibility. Subjects whose mean of the daily average pain intensity score during the preceding seven (7) days is within the protocol-defined algorithm and whose compliance with daily diary completion is adequate will be eligible for randomization. The absolute pain scores and variability among scores, as well as the actual percentage required for diary compliance, will be masked to investigators and subjects. Subject eligibility for randomization into the study based on these variables will be communicated to the investigator via the IRT system. The IRT system will notify the site if the subject is "Eligible" or "Not eligible." No other information will be provided.

Eligible subjects will be randomized to receive either NYX-2925 50 mg or placebo daily in a 1:1 allocation.

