6.11.1.3.2 Tipping Point Analysis

If the primary efficacy analysis in Section 6.11.1.2 significantly favors NYX-2925, a tipping point sensitivity analysis⁴ for the primary efficacy endpoint will be conducted to investigate how severe

the departure from the MAR assumption data must be to overturn conclusion from the primary analysis.

In this analysis, the assumption will be that that missing data in the NYX-2925 group follows a MNAR pattern. A tipping point-based approach will be used such that the trajectories of the subjects in the NYX-2925 group after early withdrawal are assumed to be worse than placebo by a fixed amount (δ). The value of δ is the adjustment added during imputation to the change from baseline NRS scores at each visit after study discontinuation. This increment is added only to the imputed change from baseline NRS scores at visits after study discontinuation of the subjects in NYX-2925. The value of δ will increase in increments of 0.1 (i.e., 0.1, 0.2, 0.3) up to the point at which the treatment difference at Week 12 is no longer statistically significant. This analysis provides a measure of the degree by which the subjects in the NYX-2925 group who discontinued early would need to be worse at each post-discontinuation visit in order for the null hypothesis of no treatment difference to no longer be rejected. Each imputed dataset produced through PROC MI procedure will be processed as follows:

- All values imputed for the placebo group will remain unchanged
- All values imputed for the NYX-2925 group will be incremented by a value of δ, which will vary from 0 up to a value by which statistical significance is not reached
- The modified data will be analyzed using similar analysis as described in Section 6.11.1.

Results will then be combined using PROC MIANALYZE and will consequently be recorded.

The "tipping point" is defined as the value of δ at which the result changes from statistically significant treatment effect to a treatment effect that is no longer statistically significant. The larger the value of δ , the more robust the conclusion from the primary analysis, with respect to assumptions around missing data.

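### Twenty imputations are too few to read the tipping point in 0.1 steps; set about 500 in both missing-data sensitivity analyses

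*SAP*

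**What the plan says.** SAP 6.11.1.3.1 (Pattern-Mixture Model) fixes the control-based imputation at "PROC MI with options nimpute=20 and seed=373613962", and a comment in its sample code repeats the number: "20 sets of results produced". Before that, an MCMC step fills intermittent gaps to make the pattern monotone. That step is drawn once (NIMPUTE=1) with the same seed.

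SAP 6.11.1.3.2 (Tipping Point Analysis) applies only if the primary analysis significantly favours NYX-2925. It adds δ to the imputed NYX-2925 values and repeats the analysis. Its rule is: "The value of δ will increase in increments of 0.1 (i.e., 0.1, 0.2, 0.3"), stopping when the Week 12 difference loses significance. It works on the datasets that PROC MI produced and names neither a number of imputations nor a seed. It tells the reader that a larger δ means a more robust conclusion.

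Protocol 12.6.1.2 planned the same search in steps of 0.5. SAP section 9, which lists changes from the protocol, does not mention the move to 0.1. Neither document gives a reason for 20, a target for Monte Carlo error, or a check with a second seed.

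**The concern.** A multiple-imputation result carries simulation noise that shrinks only as the number of imputations, m, grows. The tipping point is by definition the δ at which p is about 0.05, so this noise reaches the reported δ however strong the primary result is. If the noise exceeds what one step of δ does to the estimate, the first decimal of the reported δ partly reflects the seed. The placebo-based analysis is exposed in the same way when its p-value is close to 0.05. At stake is how precisely the study report can say how far the missing-at-random assumption may fail before a positive result is lost.

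**Working it through.** **Inputs from SAP sections 4 and 5.** "The planned sample size is a total of 204 randomized subjects", "in a 1:1 allocation", so 102 per arm; "approximately 80% power to detect a difference in means of 0.73 assuming that the common standard deviation is 1.7"; "accounting for 15% drop-out rate"; "using two-sided statistical testing with an overall Type I error rate of 0.05".

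**The plan's own figure.** A difference of 0.73 with SD 1.7 at 80% power needs 86 per arm. 86/0.85 = 101.2, rounded up to 102, so 204 in total. Power with 102 × 0.85 per arm is 0.807. The stated sample size reproduces, so these inputs are used below.

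**Effect of one δ step.** If 15% of the NYX-2925 arm lacks Week 12 data, adding 0.1 to each of their imputed values moves the arm mean by 0.1 × 0.15 = 0.015 NRS points.

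**Monte Carlo error.** The fraction of missing information (FMI) is not in the documents; 0.10 to 0.15 is assumed.
- Complete-data variance: U = (1.7 × √(2/102))² = 0.238² = 0.0567.
- Total variance: T = U/(1 − FMI).
- Between-imputation variance: B = FMI × T/(1 + 1/m).
- Monte Carlo SE of the pooled difference: √(B/m).
- Seed SD of the tipping δ: √(B/m)/0.15.

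At FMI 0.10 and m = 20: T = 0.0567/0.90 = 0.0630; B = 0.10 × 0.0630/1.05 = 0.0060; √(0.0060/20) = 0.0173; 0.0173/0.15 = 0.115.

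| m | Monte Carlo SE, FMI 0.10 to 0.15 | Seed SD of δ |
|---|---|---|
| 20 | 0.0173 to 0.0218 | 0.115 to 0.145 |
| 100 | 0.0079 to 0.0100 | 0.053 to 0.066 |
| 200 | 0.0056 to 0.0071 | 0.037 to 0.047 |
| 500 | 0.0035 to 0.0045 | 0.024 to 0.030 |

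At m = 20 the noise (0.017 to 0.022) exceeds the step (0.015). A normal central 95% spread of δ is 3.92 × 0.115 to 3.92 × 0.145, or 0.45 to 0.57. Even at an assumed FMI of 0.03 the seed SD is 0.06, more than half a step.

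**Simulation.** Trials had 102 per arm, 12 weekly values, monotone dropout spread over the weeks, and sequential regression imputation from placebo with posterior draws. δ was added to the imputed NYX-2925 values, and a Week 12 ANCOVA was pooled by Rubin's rules. For each dataset, 4,000 imputations were split into independent sets of m, each standing for one seed. Three week-to-week correlation structures were tried.
- At 15% dropout and m = 20 (FMI about 0.10 to 0.12): seed SD of δ 0.11 to 0.12, central 95% spread about 0.4, and about two thirds of sets gave a different tipping point from the large-m value. A large-m p of 0.050 ran from about 0.035 to 0.072.
- At 15% dropout and m = 200: seed SD about 0.04, spread 0.11 to 0.13, and the same p ran from about 0.046 to 0.056.
- At m = 20 with 10% and 25% dropout: spreads of 0.48 and 0.38, and p from 0.038 to 0.066 and from 0.031 to 0.083.

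**The protocol's step.** Against 0.5, a seed SD of 0.115 to 0.145 is 0.23 to 0.29 of a step. Twenty imputations are adequate for that grid.

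**The case against.** The strongest case against acting is that this is a small matter of precision. The seed is written into the SAP, so the result is repeatable and cannot be picked afterwards. The primary MMRM imputes nothing. Twenty imputations serve the pooled estimate well: at FMI 0.10 the Monte Carlo SE is 0.0173 against a pooled SE of √0.0630 = 0.251, about 7%. If the same datasets are used at every δ, the error shifts the whole curve together and the search is not erratic. The 0.1 grid can be seen as a reading increment that claims no accuracy of 0.1. Going back to 0.5 steps would also remove the mismatch.

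All of this stands as a limit on importance. A reader might infer bias, or a seed open to manipulation; the documents support neither. A reader might also infer that these two analyses settle whether the result is robust. The SAP sets no threshold for δ and no pass or fail rule, and it plans a supportive ANCOVA as well.

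What does not stand is that a fixed seed answers the point, because a repeatable number is not thereby a precise one. The SAP offers the size of δ as the evidence and chose to read it five times more finely than the protocol without raising m. Returning to 0.5 steps would not help a borderline placebo-based p-value.

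**Conclusion.** The point holds as a loss of precision in the two sensitivity analyses. At m = 20 the tipping δ has a seed SD of about 0.11 to 0.15 and a central 95% spread of about 0.4 to 0.6, or four to six of the SAP's steps.

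A reader might conclude that another seed could change δ several-fold. That is so only when the tipping point is already near zero, where most readers would call the result fragile anyway. The simulated median tipping points were about 1 to 4 NRS points, and a spread of 0.4 on those would seldom alter the reading. It matters mainly when δ is small or the placebo-based p-value is borderline.

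The sizes rest on assumptions outside the documents: the FMI, the correlation structure, dropout timing, 15% of the NYX-2925 arm lacking Week 12 data, and an ANCOVA without site in place of the MMRM. That the tipping point uses the same 20 datasets is an inference. The working also adds δ after imputation, as the bulleted steps in SAP 6.11.1.3.2 describe. The same section speaks of adding it during imputation. If the shift then carried forward from week to week, one step would move the difference by more than 0.015 and the spread in δ would be smaller.

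**What to change.** - In SAP 6.11.1.3.1, set the number of imputations to about 500. The seed SD of δ falls to about 0.024 to 0.030, so roughly 95% of seeds stay within about half a step. Two hundred is a clear improvement (0.037 to 0.048) but falls short of that.
- In SAP 6.11.1.3.2, state the same number and the seed.
- Multiply impute the monotone-making step too, for example with 500 draws there and one control-based imputation within each. Otherwise every intermittent gap still rests on a single seed-dependent draw.
- Report the Monte Carlo SE of the Week 12 difference beside the tipping δ. No m can settle a p-value that sits at 0.050, so this figure shows the reader when the side of 0.05 is uncertain.
- List the change from 0.5 to 0.1 steps in SAP section 9.

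The cost is a few lines of SAP text and code, plus computing time. A tipping point of 2.0 takes 20 steps, so about 20 × 500 = 10,000 MMRM fits instead of 20 × 20 = 400.

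### The sample code for the placebo-based sensitivity analysis fills intermittent gaps once and reuses that fill in all 20 datasets, leaving a small variance component out of the combined standard errors before Week 12

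*SAP*

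**What the plan says.** SAP 6.11.1.3.1 describes the first step as "first turning the non-monotone missing data pattern into a monotone missing pattern under the MAR assumption" and rests inference on "combined estimates using the standard multiple imputation technique", by Rubin's rules.

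The sample code reads:

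- Step 1: "PROC MI DATA=DATAIN OUT=DATAIN_MONO SEED=373613962 NIMPUTE=1", run separately by treatment, with "MCMC CHAIN=MULTIPLE IMPUTE=MONOTONE PRIOR = JEFFREYS" and the variable order "VAR BASELINE NRS_Week1-NRS_Week12".
- Step 2: "PROC MI DATA= DATAIN_MONO SEED=373613962 NIMPUTE=20", with the placebo-based MNAR model and no BY statement for the imputation number.
- Each completed dataset is analysed with the primary MMRM, and the results are "combined across all 20 imputed datasets".

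The text above the code attaches 20 imputations to the monotone-regression/MNAR step only and gives no number for the MCMC step. Protocol 12.6.1.2 names multiple imputation without any number, so nothing elsewhere corrects the code. The output is to include SEs, confidence intervals and a "p-value at each week with Week 12 as the primary timepoint of interest".

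**The concern.** Rubin's total variance is T = W + (1 + 1/M)B, where W is the mean within-imputation variance, B is the between-imputation variance and M is the number of datasets. B measures uncertainty about a missing value only if each dataset carries its own draw of it. Here every intermittent gap, and any missing baseline mean, is drawn once and is then identical in all 20 datasets. The analysis treats it as observed, both as an outcome at its own week and as a predictor of later weeks. That part of the missing data is singly imputed, which is not what the text promises.

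This is the SAP's first listed sensitivity analysis for the primary endpoint, and it reports an SE and a p-value at every week. Leaving out a variance component makes those SEs smaller than they should be, and the estimates inherit the noise of one seeded draw. The tipping-point analysis (SAP 6.11.1.3.2) starts from imputed datasets made by PROC MI and gives no imputation code of its own. If it reuses these datasets, it carries the same shared fill.

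**Working it through.** **Design figure (SAP 4).** Inputs: difference 0.73, SD 1.7, two-sided 0.05, power 80%, 15% dropout, 1:1 allocation (SAP 5). Per arm, n = 2 × (1.960 + 0.842)² × 1.7² / 0.73² = 85.1, rounded up to 86. Then 86/0.85 = 101.2, so 102 per arm and 204 in total. The plan's figure is reproduced. The documents state no SE for this sensitivity analysis, so its size has to be simulated.

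**Which values are affected.** Step 1 fills a missing weekly mean only if a later weekly mean is observed. Week 12 is last in the variable list, so a missing Week 12 value always lies in the tail and is drawn 20 times in step 2. The single fill can reach Week 12 only indirectly, through the predictors.

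**Simulation.** 102 per arm, SD 1.7, true difference 0.73, 15% dropout.

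- Step 1: within-arm multivariate-normal data augmentation with a Jeffreys prior.
- Step 2: sequential regression fitted on placebo.
- Analysis: unstructured MMRM, Rubin's rules, M = 20.
- Comparison: one step 1 fill reused 20 times, against 20 separate fills with one step 2 draw each.
- Replicates: 120 at 5% and 20% gaps, 80 at 2% and 10%.

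Assumptions not in the documents: the gap rates, gaps completely at random, uniform dropout times, high within-subject correlation (0.6 plus a decaying part), unbounded scores, no site term.

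Combined SE as coded / with 20 fills, and their ratio (from unrounded values):

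| Gap rate | Week 1 | Week 4 | Week 8 | Week 12 |
|---|---|---|---|---|
| 2% | 0.2385 / 0.2388 = 0.9985 | 0.2406 / 0.2410 = 0.9982 | 0.2441 / 0.2448 = 0.9971 | 0.2513 / 0.2515 = 0.9993 |
| 5% | 0.2386 / 0.2393 = 0.9971 | 0.2391 / 0.2397 = 0.9974 | 0.2440 / 0.2444 = 0.9982 | 0.2512 / 0.2511 = 1.0003 |
| 10% | 0.2386 / 0.2403 = 0.9927 | 0.2396 / 0.2403 = 0.9970 | 0.2422 / 0.2430 = 0.9965 | 0.2480 / 0.2482 = 0.9990 |
| 20% | 0.2371 / 0.2413 = 0.9826 | 0.2391 / 0.2416 = 0.9896 | 0.2434 / 0.2451 = 0.9927 | 0.2481 / 0.2484 = 0.9988 |

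**Why Week 1 moves.** B at Week 1 is about 0.00001 as coded at every gap rate. With 20 fills it is 0.00015, 0.00038, 0.00080 and 0.00196 for 2%, 5%, 10% and 20% gaps. At 20%, T = 0.05615 + 1.05 × 0.00196 = 0.05821, so SE = 0.2413. The omitted term is 0.00206/0.05821 = 3.5% of the variance, or about 1.8% of the SE, in line with the ratio 0.9826. The effect stays small because W (about 0.057) dominates.

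**Why Week 12 does not.** B as coded is 0.00434, 0.00408, 0.00387 and 0.00404. With 20 fills it is 0.00433, 0.00400, 0.00383 and 0.00411. The as-coded value is the larger in three of the four, so no deficit is visible.

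**Dependence on one draw.** From the Week 1 values of B, one shared fill adds noise to the estimate with SD between √0.00015 = 0.012 and √0.00196 = 0.044 NRS points, about 5% to 18% of an SE of 0.24. Averaging 20 fills divides this by √20, to about 0.003 to 0.010.

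**The case against.** The strongest reply is that nothing decisive moves.

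- **Week 12.** A separate simulation with ANCOVA at 102 per arm gave Week 12 SE ratios of 1.002 (Monte Carlo error 0.001) at 5% gaps and 0.998 (0.002) at 15%. One further ANCOVA run of 80 trials at 15% gaps gave 0.988, but it carries no Monte Carlo error and neither of the other simulations reproduced it. I do not rely on it.
- **A smaller SE need not be an anti-conservative one.** In the separate ANCOVA simulation the as-coded Week 12 SE exceeded the estimate's actual sampling SD: 0.203 against 0.177 at 5% gaps, and 0.208 against 0.176 at 15%. Week 8 was also conservative (ratio 1.05), and Weeks 1 and 4 were close to 1 at 5% gaps (0.99 and 1.01). Shortfalls appeared only at early weeks with 15% gaps (0.92 at Week 1, 0.96 at Week 4).
- **High gap rates are hard to reach.** SAP 6.2.17.1 asks for 5 of 7 diary scores at baseline, but 6.2.17.2 sets no minimum afterwards. As written, a weekly mean is missing only if all seven entries are. Randomization also requires adequate diary compliance, and sites review compliance at visits.
- **The SAP's claim of conservatism** refers to the treatment-effect estimate under the placebo trajectory, not to the SE. The single fill does not contradict it.
- **No success rule** in the SAP uses this analysis's p-value, and the primary MMRM does not impute.

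All of this stands and limits the point to low severity. It does not remove the mismatch between the code and the stated method, or the omitted variance at earlier weeks whose SEs and p-values the SAP will report.

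**Conclusion.** The code as written singly imputes the intermittent gaps, and Rubin's rules then omit their between-imputation variance. For assumed gap rates of 2% to 20%, the combined SE is understated relative to full multiple imputation by 0.15% to 1.7% at Week 1, 0.2% to 1.0% at Week 4 and 0.2% to 0.7% at Week 8. At Week 12 no effect is detectable (ratios 0.9988 to 1.0003). The gap rates and the correlation structure are assumptions. Monte Carlo errors were not recorded for the MMRM simulation, so the smallest differences should not be over-read.

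A reader might infer that the standard errors are anti-conservative at every week, Week 12 included, or that the robustness conclusion for the primary endpoint is in doubt. The documents do not support that: Week 12 is last in the imputation order, so its missing values always receive 20 draws. The primary analysis and the sample size of 204 do not depend on this code.

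**What to change.** In SAP 6.11.1.3.1:

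1. Set NIMPUTE=20 in the first PROC MI.
2. Sort DATAIN_MONO by _IMPUTATION_. Step 1 runs by treatment, so its output is not in that order and the next step would otherwise stop with a sort error.
3. Run the second PROC MI with BY _IMPUTATION_ and NIMPUTE=1.
4. Change the text to say that 20 imputations are drawn at the MCMC step, with one placebo-based draw within each.
5. State whether the tipping-point analysis uses the same datasets.

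This still yields the 20 datasets that the later code expects. It costs a few lines of code and one sentence, with no new data and no change to the sample size.

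Two separate slips in the same block can be corrected in the same edit. The MNAR list names NRS1_Week1 where the variable is NRS_Week1. The treatment differences are sorted and combined by treatment without week; run literally, that would pool all weeks into one result and matter far more than the single fill.

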11 LIST OF TABLES, FIGURES AND LISTINGS

The following table includes details of the tables, figures, and listings to be included within each section of the electronic common technical document (eCTD). The eCTD section is shown in bold. The following validation methods maybe used:

- Independent programming of values and manual review of format (IP)
- Independent programming by statistician of values and manual review of format (Stat IP)
- Manual review (MR)

Table Number	Table Title	Validation Method	Shell Number (If Repeat)
14.1	Demographics Data		
14.1.1	Disposition		
14.1.1.1	Subject Disposition, Early Withdrawals - Screened Population	IP	
14.1.1.2	Subject Disposition, Screen Failures - Screened Population	IP	
14.1.1.3	Populations by Site - Randomized Population	IP	
14.1.1.4	Protocol Deviations - Safety Population	IP	
14.1.2	Demographics		
14.1.2.1	Demographics and Baseline Characteristics - Safety Population	IP	
14.1.3	Baseline Characteristics		
14.1.3.1	Medical History Prior To Baseline by System Organ Class and Preferred Term - Safety Population	IP	
14.1.3.2	Medical History Ongoing at Baseline by System Organ Class and Preferred Term - Safety Population	IP	14.1.3.1
14.1.4.1	Medications Prior to Baseline by ATC Level 3 and Preferred Name - Safety Population	IP	
14.1.4.2	Medications Ongoing at Baseline by ATC Level 3 and Preferred Name - Safety Population	IP	14.1.4.1
14.1.5.1	Patient Global Impression of Severity at Baseline - Safety Population	IP	
14.1.6.1	Neurological Examination at Baseline - Safety Population	IP	
14.2	Efficacy Data		
14.2.1	Primary Efficacy Endpoint		
14.2.1.1.1	Primary Endpoint: Average Pain Intensity Related to DPN, Change from Baseline in Weekly Mean NRS Score, Mixed Model for Repeated Measures - Modified Intent-to-Treat Population	Stat IP	

14.2.1.1.2	Sensitivity Analysis (1): Average Pain Intensity Related to DPN, Change from Baseline to Week 12 in Weekly Mean NRS Score, Mixed Model for Repeated Measures, Imputation Using Pattern- Mixture Model - Modified Intent-to-Treat Population	Stat IP	14.2.1.1.1
14.2.1.1.3	Sensitivity Analysis (2): Average Pain Intensity Related to DPN, Change from Baseline in Weekly Mean NRS score at Week 12, Tipping Point Analysis - Modified Intent-to-Treat Population	Stat IP	
14.2.1.1.4	Supportive Analysis: Average Pain Intensity Related to DPN, Change from Baseline in Weekly Mean NRS Score at Week 12, Analysis of Covariance - Modified Intent-to-Treat Population	Stat IP	

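### The pooling code for the placebo-based imputation analysis omits week, so it cannot give the Week 12 treatment difference the SAP promises

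*SAP*

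**What the plan says.** SAP 6.11.1.3.1 imputes the primary endpoint from a placebo-based model, fits the primary MMRM to each of 20 completed datasets and pools by Rubin's rules. The prose states that "LS means and their differences between treatments will be combined across all 20 imputed datasets" and that the results will include the "estimate of treatment difference, SE, and p-value at each week with Week 12 as the primary timepoint of interest".

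The code, which the SAP presents as sample code that is to be used, runs as follows:

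- The MMRM step requests "LSMEANS TREATMENT TREATMENT*WEEK / CL DIFF".
- The LS means are sorted with "PROC SORT DATA= LSMEANS; BY TREATMENT WEEK _IMPUTATION_; RUN" and pooled by treatment and week.
- The differences are sorted with "PROC SORT DATA= DIFFS; BY TREATMENT", read in with "PROC MIANALYZE PARMS= DIFFS (WHERE=(WEEK=_WEEK" (closing brackets follow), and pooled by treatment alone.

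In the imputation step the MNAR statement reads "MNAR MODEL(NRS1_Week1-NRS_Week12", whereas the other statements use `NRS_Week1`. In SAP section 11 the output is Table 14.2.1.1.2, titled "Sensitivity Analysis (1): Average Pain Intensity Related to DPN, Change from Baseline to Week 12 in Weekly Mean NRS Score" (the title continues). It reuses the shell of the primary table, 14.2.1.1.1.

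**The concern.** Two neighbouring blocks do the same job, but only the first keeps the weeks apart. The filter on the differences drops contrasts between different weeks; it neither selects Week 12 nor separates the weeks. Without week in the BY statement, the weeks would be pooled as if they were repeated imputations of one quantity. The result would then not be the Week 12 effect, and its SE would include the change in effect over time.

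SAP section 9 (item 2) replaces the protocol's baseline-carried-forward handling with a missing-at-random assumption, and this analysis is the SAP's stress test of that assumption. It is the only missing-not-at-random multiple-imputation analysis of the primary endpoint that is run whatever the primary result. The tipping-point analysis (6.11.1.3.2) is run only if the primary result favours NYX-2925. The responder and cumulative-response analyses (6.2.17.3, 6.11.2.6) score a missing Week 12 value as non-response, but on other scales.

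**Working it through.** **Design figures (SAP 4, 5).** Difference 0.73, SD 1.7, two-sided 5%, 80% power, 15% drop-out, 1:1 allocation. n per arm = 2 × (1.960 + 0.842)² × 1.7² / 0.73² = 85.1, so 86. Then 86 / 0.85 = 101.2, so 102 per arm and 204 in total, as stated. With 102 × 0.85 = 86.7 evaluable per arm the power is 0.807. The finding does not depend on these figures; they only scale the illustration.

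**Row count (no numerical assumption).**

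- Treatment by week has 2 × 12 = 24 cells, hence 24 × 23 / 2 = 276 pairwise differences per imputation.
- The filter keeps the 12 same-week differences. All 12 carry the same first-treatment label, so BY TREATMENT cannot split them.
- As written: 12 × 20 = 240 rows in one group. If the main-effect row, whose two week fields are blank, also passes the filter: 13 × 20 = 260.
- With week in the BY statement and main-effect rows removed: 12 groups of 20, one of them Week 12.

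**What pooling over weeks estimates.** With complete data the target is the mean of the 12 weekly effects; the main-effect row does not change it.

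- Constant 0.73: 0.73.
- Linear rise to 0.73 at Week 12: 0.73 × 6.5 / 12 = 0.395, or 54% of 0.73.
- Linear fade from 0.73 at Week 1 to 0 at Week 12: 0.365, when the Week 12 effect is 0.

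For the linear rise, the shape alone adds between-row variance of (0.73/12)² × (12² − 1)/12 = 0.044 (0.041 with 260 rows). The within variance is 2 × 1.7² / 102 = 0.057. The SE is then about √(0.057 + 0.044) = 0.32, against √0.057 = 0.24 before any imputation variance.

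**Simulation (Python emulation; SAS was not run).** It assumes 102 per arm, 12 weeks, 15% monotone drop-out with last observed week uniform over 1 to 11, sequential regression imputation fitted on placebo with posterior draws, 20 imputations, unstructured covariance, and no baseline or site term. Five covariance settings were used: SD 1.7 with AR(1) 0.9, with 0.5 + 0.5 × 0.8^lag, or with compound symmetry 0.6; and SD rising from 1.0 to 1.7 with the first two correlations. There were 1,000 trials per setting (Monte Carlo SE at most 1.6 points). Ranges are across settings, and percentages are the share with p < 0.05.

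| Assumed effect | Week 12, pooled by week | p<0.05 | Pooled as written | p<0.05, 240 rows | p<0.05, 260 rows |
|---|---|---|---|---|---|
| Constant 0.73 | 0.69–0.72 | 80–84% | 0.72–0.73 | 82–96% | 83–97% |
| Linear rise to 0.73 | 0.65–0.67 | 74–78% | 0.37–0.38 | 7–12% | 9–13% |
| 0.73 to Week 8, then falling to 0 at Week 12 | 0.04–0.11 | 3–5% | 0.57–0.60 | 28–52% | 32–55% |
| Linear fade from 0.73 to 0 | 0.02–0.08 | 3–4% | 0.37–0.40 | 6–19% | 8–20% |

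Between-imputation variance was 0.005–0.007 when pooled by week and 0.010–0.072 when pooled as written.

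**Side point: one fill of intermittent gaps.** The code fills these once (`NIMPUTE=1`) before drawing 20 imputations. The omitted share of variance is f·c / (1 + f·c), where f is the assumed intermittent missingness and c the conditional variance share of Week 6 given the other weeks. With f = 0.05 and c = 0.105 this is 0.5%; with f = 0.10 and c = 0.434 it is 4.2%. A mid-study SE would be 0.3–2.1% too small. A missing Week 12 value always lies in the monotone tail, so Week 12 is touched only indirectly.

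**The case against.** The block is sample code, and it is schematic. The imputation step writes `DATA_IMPUTED` while the MMRM reads `IMPUTED_ALL`, the step between them exists only in prose, and the misnamed variable is not in the VAR list. A wrong number could arise only after that name is repaired, and only if the procedure accepts the rows. The prose leaves no doubt about the target week or the pooling. SAP 6.3.3 requires independent programming by a statistician for every analysis of the primary endpoint, checked against the SAP and the agreed shell. A single difference without a week could not fill a table built on the primary shell, for which 6.11.1.2 calls for a difference at each week. The larger figures in the table come from assumed shapes, two of them built to reach zero at Week 12.

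All of this stands, and it settles the weight. It does not remove the contradiction: the SAP says the code will be used, and the code cannot produce the output promised beside it. A gap in the PDF extraction is unlikely, because both statements are complete and the parallel LS-means block is intact. Carry-over to the tipping-point analysis is only a possibility, since 6.11.1.3.2 gives no code and names Week 12.

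**Conclusion.** The concern holds, as a minor one. That week is missing from both statements, and that no Week 12 difference, SE or p-value can result, follows from the printed code. How SAS would treat the 240 or 260 rows is inferred, not tested. If they were pooled, the error would be negligible in the estimate for a constant effect, roughly a halving for a linear rise to 0.73, and an overstatement where the effect is gone by Week 12. Those sizes rest on assumed trajectories, correlations and drop-out timing, none of which the documents give. The primary MMRM, the ANCOVA and the sample size are untouched, and the error would probably be found before reporting.

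**What to change.** In SAP 6.11.1.3.1:

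- Sort `DIFFS` by `TREATMENT WEEK _IMPUTATION_`.
- Restrict `DIFFS` to the `TREATMENT*WEEK` effect, so that main-effect rows cannot enter.
- Pool by `TREATMENT WEEK` and report the Week 12 row as the main result.
- Change `NRS1_Week1` to `NRS_Week1` in the MNAR statement.
- Optional: run the MCMC monotone step with `NIMPUTE=20`, then the MNAR step by `_IMPUTATION_` with `NIMPUTE=1`.
- If this code is reused for the tipping-point analysis, pool by week there too.

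The cost is a few lines of sample code, with no change to data or design.
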